5.2.2 Occurrence of Adverse Drug Reactions/Infections by Seriousness, Time of Onset, and Outcome

Patients included in analysis: Safety population

Analysis item: ADRs, etc.

Stratification factors: Total

Seriousness	[Serious, not serious]
Time of onset	[<7 days, 7-<28 days, 28-<56 days, 56-<84 days, 84-<168 days, >=168 days]
Outcome	[Recovered, recovering, not recovered, recovered with sequelae, died, unknown, unknown]

Analysis methods: For the aforementioned analysis item, analysis will be performed in each stratum of the stratification factor as described below.

- (1) Number of patients with an ADR, etc.
- (2) Number of ADR, etc.
- (3) Proportion of patients with an ADR, etc.
- (4) Type of ADR, etc.

For each analysis, events or patients will be counted as described below.

[Number of patients with an ADR, etc.]

- Number of patients who experienced an ADR, etc.

[Number of ADR, etc.]

- Number of reported ADR, etc. Multiple episodes of the same ADR, etc. in the same patient will be tabulated as the total number of episodes.

[Proportion of patients with an ADR, etc.]

- The proportion of patients with an ADR, etc. will be calculated as number of patients with an ADR, etc./number of patients included in safety evaluation $\times 100$.

[Type of ADR, etc.]

- ADRs, etc. will be coded using the MedDRA/J. ADRs, etc. will be classified by SOC and then tabulated by PT. For the SOC of investigations, ADRs, etc. will be sorted by HLG (lined up in ascending order of HLG code, but not output) and then tabulated by PT.
- For SOC, the number and proportion of patients with an ADR, etc. will be listed in internationally agreed SOC order. Multiple episodes of the same SOC in the same patient will be counted as 1 patient for the relevant SOC. Multiple episodes of the same SOC will be employed as 1 event according to the order of precedence described at the end.
- For PT, the number and proportion of patients with an ADR, etc. will be listed in ascending order of PT code. Multiple episodes of the same PT in the same patient will be counted as 1 patient for the relevant PT. Multiple episodes of the same PT will be employed as 1 event according to the following order of precedence:

Seriousness: serious \rightarrow not serious

Time of onset: <7 days \rightarrow 7- <28 days \rightarrow 28- <56 days \rightarrow 56- <84 days \rightarrow 84- <168 days \rightarrow ≥ 168 days

Outcome: died \rightarrow recovered with sequelae \rightarrow not recovered \rightarrow recovering \rightarrow recovered \rightarrow unknown

5.3 Occurrence of Injection Site Reaction Not Unrelated to Leuplin PRO

5.3.1 Occurrence of Injection Site Reaction Not Unrelated to Leuplin PRO

Patients included Safety population

in analysis:

Analysis item: Injection site reaction not unrelated to Leuplin PRO

Stratification factors: Specific symptom (multiple answers allowed) [Pain, pruritus, erythema, swelling, induration, abscess, ulcer, other]

Analysis methods: For the aforementioned analysis item, frequency tabulation will be performed in each stratum of the stratification factor.

5.3.2 Detail of Induration Not Unrelated to Leuplin PRO

Patients included Patients in the safety population who experienced induration not unrelated to
in analysis: Leuplin PRO

Analysis items:	Seriousness	[Serious, not serious]
	Abscess/ulcer	[No, yes]
	Size of induration (longest diameter)	[-10 mm, 11-20 mm, 21-30 mm, 31-40 mm, 41 mm-, unknown]
	Number of days from Leuplin PRO treatment to the day of onset	[<7 days, 7-<28 days, 28-<56 days, 56-<84 days, 84-<168 days, >=168 days]
	Cause of discontinuation of Leuplin PRO treatment	[Yes, no]
	Presence or absence of intervention	[No, yes]
	Outcome	[Recovered, recovering, not recovered, recovered with sequelae, died, unknown, unknown]
	Number of days from the day of onset to “recovered” or “recovering” (frequency tabulation with only patients who recovered or were recovering as the denominator)	[<7 days, 7-<28 days, 28-<56 days, 56-<84 days, 84-<168 days, >=168 days]

Analysis methods: For the aforementioned analysis items, frequency tabulation will be performed for discrete data, and summary statistics will be calculated for continuous data.

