7.4 Entry into the (Electronic) Case Report Form and Electronic Signature

The investigator or designee* shall enter patient baseline characteristics and treatment given into CCI with the investigator's electronic signature within approximately 1 month after the end of required observation at 24 weeks after the

start of Leuplin PRO treatment.

For any patient with an adverse event, the investigator or designee shall enter observation results into [CCI] with the investigator's electronic signature after monitoring the patient as long after discontinuation of treatment as possible until the adverse event is confirmed to have resolved or be resolving.

* The investigator's designee should belong to the relevant medical institution (including those under contract with the medical institution such as temporary clinical research coordinators). Before the investigator's designee begins to enter data into [CCI], a physician responsible for the surveillance (one physician per medical institution or department appointed at the time of contract) shall document the designation with the date of designation (no specific style), affix his/her signature or name and seal to the document, and submit it to Takeda's representative.

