9.5 Adverse Events (AEs)

1) Surveillance items

Presence or absence of injection site reaction, details of injection site reaction (specific symptom, date of onset, seriousness and reason for seriousness [refer to Table 2]), cause of discontinuation of Leuplin PRO treatment, intervention (presence or absence and contents), date of outcome assessment, outcome, causal relationship to Leuplin PRO [refer to Table 3]).

Presence or absence of AE other than injection site reaction (refer to Table 1), AE term, date of onset, seriousness and reason for seriousness (refer to Table

2), cause of discontinuation of Leuplin PRO treatment, intervention (presence or absence and name of the drug/intervention), date of outcome assessment, outcome, causal relationship to Leuplin PRO* (refer to Table 3)

Patients with “not resolved” or “unknown” outcome or “unevaluable” causal relationship should be followed up wherever possible.

* For the causal relationship to Leuplin PRO, the rationale for “not related” and the reason for “unevaluable” shall be collected.

Note) Additional points to consider for AEs

Abnormal worsening of target disease, for instance, worsening beyond the expected natural course of the disease, will be handled as an AE.

2) Time points of surveillance

Period from the start of Leuplin PRO treatment to 24 weeks after the start of treatment (or discontinuation of observation)

Table 1 Definition of adverse events

An AE is defined as any untoward medical occurrence in a clinical investigation subject administered a drug; it does not necessarily have to have a causal relationship with this treatment. An AE can therefore be any unfavorable or unintended sign (e.g., abnormal laboratory finding), symptom, or disease temporally associated with the use of a drug, whether or not it is considered related to the drug.

The following are also handled as AEs:

- Symptoms and so forth that occur in infants breast-fed by their mothers under treatment with a drug
- Untoward symptoms and so forth that occur in children treated with a drug
- Symptoms and so forth that occur as a result of occupational exposure to a drug
- Symptoms and so forth that occur after administration of counterfeit medicines of our ethical drugs
- Untoward symptoms that have become known to occur in drug users through lawsuits or other legal actions

Table 2 Criteria for assessing seriousness

An AE satisfying any of the following is assessed as serious:

1. Results in death (death)

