1.5 Other Handling

- Time of onset of AE (or ADR, etc.): Time of onset of AE (or ADR, etc.) will be calculated as date of onset of AE (or ADR, etc.) - start date of Leuplin PRO treatment + 1. If the day of AE (or ADR, etc.) is unknown, 1 will be used for calculation. If an AE (or ADR, etc.) occurs in the same year and month as Leuplin PRO treatment is started, the start date of Leuplin PRO treatment will be used for calculation.
- Premenopausal breast cancer drugs other than LH-RH agonists and premenopausal breast cancer drugs other than Leuplin PRO will be classified using drug codes according to Attached table 2.

2 Number of Surveillance Medical Institutions, Number of Enrolled Patients, and Patient Composition

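### SAP 5.3.2 pools recovered and still-recovering indurations in one days-from-onset row and names no end date, so the row cannot be read as induration duration (minor)

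*SAP*

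**What the plan says.** - **SAP 5.3.2**, for patients with induration not ruled unrelated to the drug, includes the item "Number of days from the day of onset to “recovered” or “recovering". It is a "frequency tabulation with only patients who recovered or were recovering as the denominator", in six classes from under 7 days to 168 days or more. Outcome is a separate item in the same section.
- **Protocol 9.5** lists for injection site reactions "details of injection site reaction (specific symptom, date of onset, seriousness and reason for seriousness" and, at the other end of the event, "date of outcome assessment, outcome, causal relationship to Leuplin PRO [refer to Table 3". No date of recovery is listed.
- **Protocol 7.4** has the investigator monitor an adverse event "until the adverse event is confirmed to have resolved or be resolving". Protocol 9.5 adds: "Patients with “not resolved” or “unknown” outcome or “unevaluable” causal relationship should be followed up wherever possible". An event that is resolving is not in that list.
- **SAP 1.5** defines time of onset (onset date minus treatment start, plus 1) and an incomplete-date rule: "If the day of AE (or ADR, etc.) is unknown, 1 will be used for calculation". It has no corresponding rule for the interval from onset to outcome.

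**The concern.** An item that runs from onset to recovery invites the reader to see how long induration lasts. Two features of the plan prevent that reading. The end of the interval is undefined, and the one end date the protocol lists records when someone looked, which need not be when the lesion went. In addition, a lesion may leave follow-up while still present and then enter the same row as one that has gone.

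The surveillance was set up because a single dose contains twice as much drug as the comparator formulation and has a different concentration profile. Injection site reaction is the reaction that protocol 3.2 names first, and SAP 5.3.2 and 5.3.3 single out induration. This row is the SAP's only duration-type result for induration. If it is taken as lesion duration, part of what it shows would be visit timing and the point at which follow-up ended.

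**Working it through.** **1. The plan's own figure.** The documents state no figure for induration duration. The one figure that can be reproduced is the sample size: 1 − 0.99^300 = 0.951, and the smallest n giving at least 0.95 is 299, so 300 holds. It does not bear on this point.

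**2. What can be computed.** Let O be the onset date, A the outcome assessment date, B the date the lesion began recovering and R the date it was gone (B ≤ R). From the listed fields, D = A − O.

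- Recorded as recovered, with A a visit date: A ≥ R, so D ≥ R − O. D is an upper limit on time to resolution.
- Recorded as recovering: B ≤ A < R, so D < R − O. D is a lower limit on time to resolution.
- Against the SAP's literal item, where reaching either state counts: A cannot precede the state it records, so the error is zero or upward.

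The pooled row thus combines upper and lower limits on the same quantity without marking which is which.

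**3. Hand example (visit times assumed).** Induration starts on day 7 and is gone on day 28, so it lasts 28 − 7 = 21 days.

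| Recovery assessed on | D (days) | SAP class |
|---|---|---|
| day 28 | 28 − 7 = 21 | 7 to <28 |
| day 84 | 84 − 7 = 77 | 56 to <84 |
| day 168 | 168 − 7 = 161 | 84 to <168 |

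Adding 1, as SAP 1.5 does for onset, gives 22, 78 and 162, in the same classes. In the other direction, a lesion called recovering 14 days after onset that in fact lasts 100 days enters as 14 (7 to <28), while its time to resolution belongs in 84 to <168. That is a shortfall against resolution, but not against the literal item.

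**4. Simulation (all inputs assumed).** Time to resolution is exponential with median 28, 56 or 84 days. Recovering begins at half that time. Visits come every 14, 28, 56 or 84 days, with a random first visit. Follow-up stops at the first visit showing recovering or recovered. The four extreme combinations are:

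| Median (days) | Visit gap (days) | Recorded recovering | Recovering: mean days short of resolution | Recovered: mean days beyond resolution | Different class from true resolution | Mean excess over literal item (days) |
|---|---|---|---|---|---|---|
| 28 | 14 | 72% | 20 | 5 | 50% | 7 |
| 28 | 84 | 24% | 20 | 35 | 71% | 42 |
| 84 | 14 | 89% | 60 | 5 | 66% | 7 |
| 84 | 84 | 54% | 60 | 31 | 55% | 42 |

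Over all twelve combinations, 24% to 89% of records are recovering and fall short of resolution by a mean of 20 to 61 days. Recovered records overshoot by a mean of 5 to 35 days, and 50% to 71% of all records land in a different class from true resolution. The excess over the literal item is never negative and averages half the visit gap (14/2 = 7 up to 84/2 = 42 days). If every lesion were instead followed to full resolution, the mean overshoot would also be 7 to 42 days, with 17% to 79% in a different class.

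**The case against.** A reader might infer more than the documents support, in three ways.

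- *The interval cannot be derived.* It can: onset to outcome assessment is computable from listed fields. What is missing is a statement of the end date and of what the interval means.
- *The result is wrong in both directions.* That is true only if the target is full resolution. The SAP names recovering as an endpoint in the label and in the denominator, and against that wording no record understates.
- *Only the assessment date was collected, so the table will be wrong.* The case report form is not among the documents. SAP 5.3.2 tabulates induration size, which protocol 9.5 does not list, so the form holds more than that list and may hold a recovery date. The assessment date is also undefined: if sites enter the day the outcome was reached, recovered records carry no error.

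The other side can add that protocol 3.2 asks for time of onset, incidence and seriousness, not duration. The separate outcome item shows how many lesions were recovered and how many recovering. An outcome assessed only at week 24 also fits poorly with an observation schedule that marks injection site reaction as followed throughout the period.

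All of this stands and limits the size of the point. It does not remove it. The outcome item gives the overall mix but not which day classes the still-present lesions occupy. Even with a true recovery date on the form, the recovering records would remain lower limits pooled with completed durations.

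**Conclusion.** The point holds as a minor one. SAP 5.3.2 sets a pooling rule under which the row cannot be read as induration duration, and it leaves the end date unstated. That a recovering interval is a lower limit follows from the documents. That a recovered interval is an upper limit rests on the assumption that the assessment date is a visit date. The class shifts and day counts above rest on assumed visit patterns and lesion durations; they show what could happen, not what the data will show. The effect is confined to one row of one descriptive table. Incidence, time of onset, seriousness and the sample size of 300 do not depend on it.

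**What to change.** In SAP 5.3.2:

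1. Tabulate the interval in two columns, one for recovered and one for recovering, and label the second as lesion still present at last assessment.
2. Name the item as days from onset to the date of outcome assessment. If the case report form holds a true recovery date, use that date for the recovered column and say so.
3. In the same line, state how an incomplete end date is handled, since SAP 1.5 covers onset only.

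No new data are needed. This matters because the SAP is dated 4 April 2019, after the registration dates in protocol section 8. The cost is a change of wording, one extra column in one table, and a duration statement made of limits where a single distribution would look tidier.

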5.3.3 Incidence of Induration Not Unrelated to Leuplin PRO by Factor

Patients included	Safety population	
in analysis:		
Analysis item:	Induration not unrelated to Leuplin PRO	
Stratification	Age (years)	[<35 years, >=35 years, unknown]
factors:	BMI (kg/m ²)	[<18.5, 18.5-<25.0, 25.0-<30.0, >=30.0, unknown]
	Full-treatment status of Leuplin PRO	[Yes, no]
	Injection site	[Extensor surface of the upper arm, deltoid region of the upper arm, abdomen, buttocks, other]
	Presence or absence of predisposition to hypersensitivity	[No, yes, unknown]
	Presence or absence of concurrent allergic disease	[No, yes]
	Disposition of allergic disease	[Bronchial asthma, pollinosis, allergic rhinitis, allergic dermatitis]
	Presence or absence of treatment with LH-RH agonist immediately before the start of Leuplin PRO treatment	[No, yes]
	Disposition of treatment with LH-RH agonist immediately before the start of Leuplin PRO treatment	[Leuprorelin acetate 3.75 mg, leuprorelin acetate 11.25 mg, goserelin 3.6 mg, goserelin 10.8 mg]
Analysis methods:	For the aforementioned analysis item, analysis will be performed in each stratum of the stratification factor as described below.	
	(1) Number of patients with induration not unrelated to Leuplin PRO and incidence of induration not unrelated to Leuplin PRO	

5.4 Occurrence of Adverse Drug Reactions/Infections by Baseline Characteristics and Treatment Given

5.4.1 Occurrence of Adverse Drug Reactions/Infections by Baseline Characteristics and Treatment Given

Patients included in analysis:	Safety population	
Analysis item:	ADRs, etc.	
Stratification factors:	Age (years)	[<35 years, >=35 years, unknown]
	ECOG Performance Status	[0, 1, 2, 3, 4]
	Full-treatment status of Leuplin PRO	[Yes, no]
	Injection site	[Extensor surface of the upper arm, deltoid region of the upper arm, abdomen, buttocks, other]
	Disease status	[Patient on preoperative adjuvant therapy, patient on postoperative adjuvant therapy, patient with advanced breast cancer, patient with recurrent breast cancer]
	Presence or absence of predisposition to hypersensitivity	[No, yes, unknown]
	Presence or absence of concurrent renal impairment	[No, yes]
	Presence or absence of concurrent hepatic impairment	[No, yes]
	Presence or absence of concurrent lifestyle diseases	[No, yes]
	Presence or absence of concurrent allergic disease	[No, yes]
	Presence or absence of history of thromboembolism	[No, yes, unknown]
	BMI (kg/m ²)	[<18.5, 18.5-<25.0, 25.0-<30.0, >=30.0, unknown]
	Presence or absence of treatment with LH-RH agonist immediately before the start of Leuplin PRO treatment	[No, yes]

Presence or absence of treatment with [No, yes]
premenopausal breast cancer drug
other than LH-RH agonists
immediately before the start of Leuplin
PRO treatment

Analysis
methods:

For the aforementioned analysis item, analysis will be performed in each stratum
of the stratification factor as described below.

(1) Number of patients with an ADR, etc. and incidence of ADR, etc.

5.4.2 Occurrence of Adverse Drug Reactions/Infections by Age Group

Patients included Safety population
in analysis:
Analysis item: ADRs, etc.
Stratification Age (years) [<35 years, ≥ 35 years, unknown]
factor:
Analysis For the aforementioned analysis item, analysis as described in Section 5.1.2 will
methods: be performed in each stratum of the stratification factor.

5.4.3 Occurrence of Adverse Drug Reactions/Infections by ECOG Performance Status

Patients included Safety population
in analysis:
Analysis item: ADRs, etc.
Stratification ECOG Performance Status [0, 1, 2, 3, 4]
factor:
Analysis For the aforementioned analysis item, analysis as described in Section 5.1.2 will
methods: be performed in each stratum of the stratification factor.

5.4.4 Occurrence of Adverse Drug Reactions/Infections by Full-Treatment Status of Leuplin PRO

Patients included Safety population
in analysis:
Analysis item: ADRs, etc.
Stratification Full-treatment status of Leuplin PRO [Yes, no]
factor:
Analysis For the aforementioned analysis item, analysis as described in Section 5.1.2 will
methods: be performed in each stratum of the stratification factor.

5.4.5 Occurrence of Adverse Drug Reactions/Infections by Injection Site

Patients included Safety population
in analysis:
Analysis item: ADRs, etc.
Stratification Injection site [Extensor surface of the upper arm,
factor: deltoid region of the upper arm,
abdomen, buttocks, other]
Analysis For the aforementioned analysis item, analysis as described in Section 5.1.2 will
methods: be performed in each stratum of the stratification factor.

5.4.6 Occurrence of Adverse Drug Reactions/Infections by Disease Status

Patients included Safety population
in analysis:
Analysis item: ADRs, etc.
Stratification Disease status [Patient on premenopausal adjuvant
factor: therapy, patient on postoperative
adjuvant therapy, patient with
advanced breast cancer, patient with
recurrent breast cancer]
Analysis For the aforementioned analysis item, analysis as described in Section 5.1.2 will
methods: be performed in each stratum of the stratification factor.

5.4.7 Occurrence of Adverse Drug Reactions/Infections by Presence or Absence of Predisposition to Hypersensitivity

Patients included Safety population
in analysis:
Analysis item: ADRs, etc.
Stratification Presence or absence of predisposition [No, yes, unknown]
factor: to hypersensitivity
Analysis For the aforementioned analysis item, analysis as described in Section 5.1.2 will
methods: be performed in each stratum of the stratification factor.

5.4.8 Occurrence of Adverse Drug Reactions/Infections by Presence or Absence of Concurrent Renal Impairment

Patients included Safety population
in analysis:
Analysis item: ADRs, etc.
Stratification Presence or absence of concurrent [No, yes]
factor: renal impairment
Analysis For the aforementioned analysis item, analysis as described in Section 5.1.2 will
methods: be performed in each stratum of the stratification factor.

5.4.9 Occurrence of Adverse Drug Reactions/Infections by Presence or Absence of Concurrent Hepatic Impairment

Patients included Safety population
in analysis:
Analysis item: ADRs, etc.

Stratification factor: Presence or absence of concurrent hepatic impairment [No, yes]

Analysis methods: For the aforementioned analysis item, analysis as described in Section 5.1.2 will be performed in each stratum of the stratification factor.

5.4.10 Occurrence of Adverse Drug Reactions/Infections by Presence or Absence of Concurrent Lifestyle Diseases

Patients included in analysis: Safety population

Analysis item: ADRs, etc.

Stratification factor: Presence or absence of concurrent lifestyle diseases [No, yes]

Analysis methods: For the aforementioned analysis item, analysis as described in Section 5.1.2 will be performed in each stratum of the stratification factor.

5.4.11 Occurrence of Adverse Drug Reactions/Infections by Presence or Absence of Concurrent Allergic Disease

Patients included in analysis: Safety population

Analysis item: ADRs, etc.

Stratification factor: Presence or absence of concurrent allergic disease [No, yes]

Analysis methods: For the aforementioned analysis item, analysis as described in Section 5.1.2 will be performed in each stratum of the stratification factor.

5.4.12 Occurrence of Adverse Drug Reactions/Infections by Presence or Absence of History of Thromboembolism

Patients included in analysis: Safety population

Analysis item: ADRs, etc.

Stratification factor: Presence or absence of history of thromboembolism [No, yes, unknown]

Analysis methods: For the aforementioned analysis item, analysis as described in Section 5.1.2 will be performed in each stratum of the stratification factor.

